7.3.2 Secondary endpoint analyses

Part A:

[figure not shown]
- The number of patients with DLTs during the entire on-treatment period will be presented in a summary table.
- PK parameters will be analysed as described in Section 7.3.5.
- OR based on RECIST v1.1 will be analysed descriptively in terms of objective response rate, defined as the proportion of patients with objective response.

Part B:

- The number of patients with DLTs during the entire on-treatment period will be presented in a summary table.
- PK parameters will be analysed as described in Section 7.3.5.
- OR will be analysed descriptively in terms of ORR, defined as the proportion of patients with OR based on RECIST v1.1.

Part C:

- Duration of OR (based on RECIST v1.1) will analysed descriptively.

7.3.4 Safety analyses

Adverse events will be coded using the Medical Dictionary for Drug Regulatory Activities (MedDRA). Standard BI summary tables and listings will be produced. All adverse events

with an onset between start of treatment and end of the residual effect period (REP), a period of 30 days after the last dose of trial medication, will be assigned to the on-treatment period for evaluation.

All treated patients will be included in the safety analysis. In general, safety analyses will be descriptive in nature and will be based on BI standards. No hypothesis testing is planned.

Statistical analysis and reporting of adverse events will concentrate on treatment-emergent adverse events, i.e. all adverse events occurring between start of treatment and end of the residual effect period. Adverse events that start before first drug intake and deteriorate under treatment will also be considered as 'treatment-emergent'.

Frequency, severity, and causal relationship of adverse events will be tabulated by system organ class and preferred term after coding according to the current version of the MedDRA at the database lock.

Laboratory data will be analysed both quantitatively as well as qualitatively. The latter will be done via comparison of laboratory data to their reference ranges. Values outside the reference range as well as values defined as clinically relevant will be summarised. Treatment groups will be compared descriptively with regard to distribution parameters as well as with regard to frequency and percentage of patients with abnormal values or clinically relevant abnormal values.

Vital signs, physical examinations, or other safety-relevant data observed at screening, baseline, during the course of the trial and at the end-of-trial evaluation will be assessed with regard to possible changes compared to findings before start of treatment.

Analyses of the centrally evaluated ECG data will be specified in the TSAP.

7.3.5 Pharmacokinetic and pharmacodynamic analyses

The pharmacokinetic parameters listed in Section 5.3.1 and Appendix 10.4 will be calculated according to the relevant BI internal procedures.

Only concentration values within the validated concentration range and actual sampling times will be used for the calculation of pharmacokinetic parameters. Concentrations used in the pharmacokinetic calculations will be in the same format provided in the bioanalytical report, (that is, to the same number of decimal places provided in the bioanalytical report).

The following descriptive statistics will be calculated for plasma concentrations and PK parameters: number (N), arithmetic mean, standard deviation, minimum, median, maximum, arithmetic coefficient of variation, geometric mean, and geometric coefficient of variation. The exception to this is t_{max} , where only median, minimum and maximum will be calculated. The data format for descriptive statistics of concentrations will be identical to the data format of the respective concentrations. Thereafter, the individual values, as well as the descriptive statistics, will be reported with three significant digits in the clinical trial report.

For handling of missing data, please refer to Section 7.5.

Analyses will be carried out using Phoenix® WinNonlin® 6.3 (or later) and/or SAS® software, Version 9.4 (or later).

7.4 INTERIM ANALYSES

The Sponsor will continuously monitor the safety. The dose escalation design in parts A and B foresees that the Sponsor and the SRC perform regular safety evaluations. These evaluations will be unblinded to dose.

If considered necessary, as soon as the MTDs in Part A and Part B are determined or when the highest dose levels are reached, evaluations of the safety and other relevant aspects will be performed. Results of these evaluations will be documented and archived. If needed, each part will be analysed and reported in separate clinical trial reports. If applicable, such analyses will be defined in more detail in the TSAP.

An interim futility analysis will be performed by the SRC in Part C after 20 patients have been treated for at least 18 weeks. Until a decision from this futility analysis is made, the enrolment for that trial part will not be stopped. Enrolment will only be stopped if the defined efficacy boundary (see Table 7.7: 1) is not met. The SRC will document the decision, whether the futility bound is met or not in the SRC meeting minutes.

7.5 HANDLING OF MISSING DATA

No imputation will be performed on missing efficacy data. Missing baseline laboratory values will be imputed by the respective values from the screening visit. No other imputations will be performed on missing data although every effort will be made to obtain complete information on all adverse events, with particular emphasis on potential DLTs.

Plasma concentration - time profiles

Concentration data identified with NOS (no sample), NOR (no valid result), NOA (not analyzed), and BLQ (below the limit of quantification) will be ignored and not replaced by zero at any time point (applies also to the lag phase). Descriptive statistics of concentrations at specific time points will be calculated only when at least 2/3 of the individuals have concentrations within the validated concentration range. The overall sample size to decide whether the “2/3 rule” is fulfilled will be based on the total number of samples intended to be drawn for that time point (i.e., BLQ, NOR, NOS, NOA are included).

Pharmacokinetic parameters

In the non-compartmental analysis, concentration data identified with NOS, NOR, and NOA will not be considered. BLQ values in the lag phase will be set to zero. The lag phase is defined as the period between time zero and the first time point with a concentration above the quantification limit. All other BLQ values of the profile will be ignored.

Every effort will be made to include all concentration data in an analysis. If not possible, a case-to-case decision is required whether the value should only be excluded from half-life estimation or the complete analysis.

- If a concentration is only excluded from half-life determination, it will be used for all other calculations (e.g., descriptive statistics) and for graphical presentation.
- If a concentration value is excluded from all calculations, it will not be presented graphically or used for the calculation of descriptive statistics and parameter determination. However, the excluded concentration itself will be listed in the tables in Section 15 of the clinical trial report associated with an appropriate flag.

Descriptive statistics of parameters are calculated only when at least 2/3 of the individual parameter estimates of a certain parameter are available. If the actual sampling time is not recorded or is missing for a certain time point, the planned time will generally be used for this time point instead. Pharmacokinetic parameters which cannot be determined will be identified by "not calculated" (NC).

7.6 RANDOMISATION

No randomisation will be performed. In Part A and Part B, patients will be assigned to escalating dose groups by order of admission into the trial. In Part C, patients will be assigned to the expansion cohorts according to their diagnosis.

7.7 DETERMINATION OF SAMPLE SIZE

The number of patients to be enrolled in Part A and B cannot be predicted. Only estimation is provided in this section.

Part A:

No formal statistical power calculations to determine sample size were performed for this trial part. Approximately 30 patients (including patients at the MTD) are expected to be enrolled into Part A of this trial based on the number of dose levels/cohorts that are tested. Fewer patients might be needed based on the recommendation of the SRC and the criteria specified (see Section 8.7). However, the actual number of patients will depend on the number of dose cohorts tested. Based on the simulation study to evaluate operating characteristics of the BLRM (see statistical appendix), at least 20 evaluable patients (where evaluable patients refer to patients not fulfilling the criteria for replacement [Section 3.3.4.4]) are expected to be treated in the dose escalation part for the model to have reasonable operating characteristics relating to its MTD recommendation.

Part B:

No formal statistical power calculations to determine sample size were performed for this trial part. Approximately 31-37 patients (including patients at the MTD) will be expected for this part based on the number of dose levels/cohorts that are tested. Fewer patients might be needed based on the recommendation of the SRC and the criteria specified (see Section 8.7). However, the actual number of patients will depend on the number of dose cohorts tested.

Part C NSCLC:

A justification of the cohort size for this expansion cohort is based on assumed OR rates. A futility check will be performed by the SRC when 20 evaluable patients have been treated for at least 18 weeks. If an efficacy signal, i.e. at least 2 patients with OR, is observed out of 20 evaluable patients, the total intended 40 evaluable patients will be recruited into this trial part. If this efficacy signal cannot be observed, enrolment into the trial will be stopped.

Table 7.7: 1 summarises the probabilities to stop the trial after the futility analysis assuming different true underlying OR rates.

Table 7.7: 1 Probabilities to stop the trial at the futility analysis

Assumed true OR rate (%)	Cohort size	P(< 2 patients with OR)	P(\geq 2 patients with OR)
10	20	0.39	0.61
30	20	0.01	0.99
45	20	<0.01	>0.99

Table 7.7: 2 displays the probability of observing at least 2 patients with OR in the first 20 evaluable patients and then observing a certain number of patients with OR out of a total of 40 evaluable patients given different assumed true underlying OR rates. For example, assuming a true underlying OR rate of 10%, the probability to observe 2 or more patients with OR out of 20 evaluable patients is 0.61. This means that the probability to stop the trial is 0.39 in this scenario. Overall, the probability to observe 4 patients with OR out of 40 patients, given that at least 2 patients with OR had been seen already in the first 20 patients, is only 0.473 which is considered as acceptable for this trial.

Assuming a true underlying OR rate of 45%, the probability to observe 2 or more patients with OR out of 20 patients is almost 1. Overall, the probability to observe 18 patients with OR out of 40 patients, given that at least 2 patients with OR had been seen already in the first 20 patients, is 0.561 which is considered satisfactory for this trial.

Table 7.7: 2 Probabilities for objective response rates of the expansion cohort under different assumptions given the trial has not been stopped at the futility analysis

Assumed true OR rate (%)	Cohort size	At least 2 patients with OR in the first 20 patients and probability to observe at least 18 patients with OR in total						
		4	8	10	12	14	16	18
10	40	0.473	0.041	0.005	< 0.001	< 0.001	< 0.001	< 0.001
30	40	0.992	0.942	0.803	0.559	0.297	0.115	0.032
45	40	>0.999	>0.999	0.997	0.982	0.925	0.786	0.561

Probabilities in [Table 7.7: 2](#) are calculated as $P(n_1 + n_2 \geq c \text{ AND } n_1 \geq 2)$, where n_1 is the number of patients with OR out of the first 20 patients, n_2 is the number of additional patients with OR after more patients are enrolled after the futility check. c is the required minimum number of patients with OR displayed in [Table 7.7: 2](#) (i.e. 4, 8, 10, 12, 14, 16, or 18 respectively). The calculations in this section were performed using R version 3.5.1. It is assumed that 44 patients need to be enrolled in order to end up with 40 evaluable patients for the primary analysis.

8. INFORMED CONSENT, TRIAL RECORDS, DATA PROTECTION, PUBLICATION POLICY, AND ADMINISTRATIVE STRUCTURE

The trial will be carried out in compliance with the protocol, the ethical principles laid down in the Declaration of Helsinki, in accordance with the ICH Harmonized Tripartite Guideline for Good Clinical Practice (GCP), relevant BI Standard Operating Procedures (SOPs), and other relevant regulations.

Standard medical care (prophylactic, diagnostic and therapeutic procedures) remains the responsibility of the treating physician of the patient.

The Investigator will inform the Sponsor immediately of any urgent safety measures taken to protect the trial patients against any immediate hazard, as well as of any serious breaches of the protocol or of ICH GCP.

The BI transparency and publication policy can be found on the following web page: trials.boehringer-ingelheim.com. The rights of the Investigator and of the Sponsor with regard to publication of the results of this trial are described in the investigator contract. As a rule, no trial results should be published prior to finalization of the Clinical Trial Report.

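### Protocol Section 7.7 describes the figures in Table 7.7: 2 as conditional on passing the Part C futility look, but they are joint probabilities of passing and reaching at least c responders

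*Protocol*

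**What the plan says.** The Part C rule in Protocol Section 7.7 is a single futility look. "If an efficacy signal, i.e. at least 2 patients with OR, is observed out of 20 evaluable patients", then "the total intended 40 evaluable patients will be recruited into this trial part"; otherwise enrolment stops. For the lowest rate considered, the section states that "assuming a true underlying OR rate of 10%, the probability to observe 2 or more patients with OR out of 20 evaluable patients is 0.61". It adds: "This means that the probability to stop the trial is 0.39 in this scenario".

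Table 7.7: 2 then gives probabilities for c = 4, 8, 10, 12, 14, 16 and 18 responders in 40 patients, at true rates of 10%, 30% and 45%. The section describes these figures in two ways.

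- **As conditional.** The table title says the probabilities are "under different assumptions given the trial has not been stopped at the futility analysis". The 10% example speaks of 4 responders in 40, "given that at least 2 patients with OR had been seen already in the first 20 patients, is only 0.473", and calls this acceptable. The 45% example refers to "the probability to observe 18 patients with OR out of 40 patients" under the same condition, gives 0.561 and calls it satisfactory.
- **As joint.** The sentence introducing the table speaks of passing the look and then seeing some number of responders. The column heading also joins the two events with *and*. The formula under the table is P(n1 + n2 ≥ c AND n1 ≥ 2), where n1 and n2 are the responders before and after the look and c is a minimum count.

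The heading also names at least 18 responders, although it stands over all seven columns.

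**The concern.** A probability given that futility was passed and a probability of passing futility and then reaching a count are different quantities. They separate most where the chance of passing is lowest, which here is the 10% row. That is also the row in which the sponsor attaches a judgement of acceptability to a figure.

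A reader who relies on the title and the worked example would believe that, at a true rate of 10%, a cohort that has passed the look reaches 4 of 40 responses a little less than half the time. The two examples also leave out *at least*, so they literally describe exact counts, which the figures are not. What is at stake is a correct statement of the operating characteristics in the cohort-size justification.

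**Working it through.** **Inputs** (all from Protocol Section 7.7): 20 patients before the look; continue if n1 ≥ 2; 40 patients in total, so 20 more after the look; true rates p = 10%, 30% and 45%. I take n1 and n2 as independent Binomial(20, p).

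**1. Probability of passing, p = 10%.**
P(n1 ≥ 2) = 1 − 0.9^20 − 20 × 0.1 × 0.9^19 = 1 − 0.1216 − 0.2702 = 0.608.
This matches the 0.61 (and 0.39 for stopping) in Table 7.7: 1. At 30% and 45% it is 0.9924 and 0.9999.

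**2. Reproducing 0.473 as the joint probability, c = 4, p = 10%.**
P(n1 ≥ 2 and n1 + n2 ≥ 4) = P(n1 = 2) × P(n2 ≥ 2) + P(n1 = 3) × P(n2 ≥ 1) + P(n1 ≥ 4)
= 0.2852 × 0.6083 + 0.1901 × 0.8784 + 0.1330
= 0.1735 + 0.1670 + 0.1330 = 0.473.
The same joint calculation reproduces every cell of the table, including 0.041 and 0.005 at 10%, 0.942 and 0.803 at 30% (c = 8 and 10), and 0.561 at 45% (c = 18).

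**3. The conditional values** are joint ÷ P(n1 ≥ 2).

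| True rate | c | Joint (printed) | Conditional on passing |
|---|---|---|---|
| 10% | 4 | 0.473 | 0.4734 / 0.6083 = 0.778 |
| 10% | 8 | 0.041 | 0.0412 / 0.6083 = 0.068 |
| 10% | 10 | 0.005 | 0.0050 / 0.6083 = 0.008 |
| 30% | 4 | 0.992 | 0.9921 / 0.9924 = 0.9997 |
| 30% | 8 | 0.942 | 0.9419 / 0.9924 = 0.949 |
| 45% | 18 | 0.561 | 0.5609 / 0.9999 = 0.561 |

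The largest shift in the 30% row is 0.9997 − 0.9921 = 0.0076. In the 45% row every shift is below 0.001.

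**4. Exact counts, as the two examples are literally worded.** Exactly 4 responders at 10%: joint 0.144, conditional 0.1436 / 0.6083 = 0.236. Exactly 18 at 45%: 0.126. None of these is the printed 0.473 or 0.561.

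**5. No look at all.** P(at least 4 of 40) at 10% is 0.577, which is not the printed figure either. Of the readings tried, only the joint, at-least-c one fits.

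**The case against.** The strongest reply is that no printed number is wrong. The formula stands directly under the table and defines c as a minimum, and the introductory sentence and the column heading also read as joint. A careful reader can recover the right meaning without leaving the section. This stands, and it makes the fault one of labelling, not of calculation.

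The reply goes further. The joint probability is the proper pre-trial operating characteristic of a design with a futility stop, because it gives credit for stopping early. So 0.473 is the relevant figure to call acceptable. This also stands.

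A reader might still infer that the sponsor accepted 0.473 when the true figure is 0.778, and that Part C separates 10% from higher rates worse than claimed. The documents do not support that:

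- The 0.778 answers a different question, about cohorts already past the look. Reaching it also means keeping the conditional wording while correcting 4 to at least 4. The fully literal sentence gives 0.236, which errs the other way.
- No success threshold is set at 4 of 40, which is simply an observed rate of 10%. Sections 7.1.3 and 7.2 say that the Part C analysis is descriptive and that there is no formal test.
- Even on the conditional scale, the 10% row falls to 0.068 at c = 8 and 0.008 at c = 10. At a true rate of 30% the corresponding values are 0.949 and 0.809 (0.8033 / 0.9924).

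What the reply does not remove is the contradiction. The title and both worked examples state a property that the figures do not have, and the sponsor's judgement is attached to one of those sentences.

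**Conclusion.** Wrong as written, as a mis-described operating characteristic; low severity. Section 7.7 contradicts itself on what Table 7.7: 2 shows. The values are correct as joint probabilities of passing futility and observing at least c responders. The title and both examples, which call them conditional, are not correct, and neither is the heading that names 18 over all columns.

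The mislabelling has a material size only in the 10% row, chiefly at c = 4 (0.473 joint, 0.778 conditional). The result rests on independent binomial counts in the two halves of the cohort and on exactly 20 + 20 evaluable patients, which is the set-up that reproduces the protocol's own table.

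The futility rule, the 40 evaluable patients and the 44 to be enrolled are unaffected. SAP Section 4 reports that Part C was cancelled and enrolled no patients, so no analysis or patient is touched. What remains is the accuracy of the stated design property.

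**What to change.** In Section 7.7:

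1. Retitle Table 7.7: 2 as the probability of passing the futility analysis and observing at least c patients with objective response.
2. In both worked examples, replace the conditional phrase with *and*, and write *at least 4* and *at least 18*.
3. Change the column heading to *at least c*.

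The figure 0.473 and the sponsor's judgement on it can then stay as they are. If the chance after passing the look is also of interest, 0.778 can be added as a separate figure labelled as conditional on continuing.

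The cost is a few words. No printed probability, decision rule or sample size changes.

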8.1 TRIAL APPROVAL, PATIENT INFORMATION, INFORMED CONSENT

This trial will be initiated only after all required legal documentation has been reviewed and approved by the respective IRB and competent authority according to national and international regulations. The same applies for the implementation of changes introduced by amendments.

Prior to patient participation in the trial, written informed consent must be obtained from each patient (or the patient's legally accepted representative) according to ICH / GCP and to the regulatory and legal requirements of the participating country. Each signature must be personally dated by each signatory and the informed consent and any additional patient-information form retained by the Investigator as part of the trial records. A signed copy of the informed consent and any additional patient information must be given to each patient or the patient's legally accepted representative.

The Investigator or delegate must give a full explanation to trial patients based on the patient information form. A language understandable to the patient should be chosen, technical terms and expressions avoided, if possible.

The patient must be given sufficient time to consider participation in the trial. The Investigator or delegate obtains written consent of the patient's own free will with the informed consent form after confirming that the patient understands the contents. The Investigator or his/her delegate must sign (or place a seal on) and date the informed consent form. If a trial collaborator has given a supplementary explanation, the trial collaborator also signs (or places a seal on) and dates the informed consent.

Re-consenting may become necessary when new relevant information becomes available and should be conducted according to the Sponsor's instructions. The consent and re-consenting process should be properly documented in the source documentation.

Following the initial radiologic progression, patients may be allowed to continue on treatment if, in the opinion of the Investigator, they are experiencing clinical benefit and criteria for withdrawal are not met (see Section 3.3.4.1). In this case, an additional informed consent form specific for this circumstance will be signed by the patient prior to treatment continuation.

8.2 DATA QUALITY ASSURANCE

A quality assurance audit/inspection of this trial may be conducted by the Sponsor, Sponsor's designees, or by an IRB or by regulatory authorities. The quality assurance auditor will have access to all medical records, the Investigator's trial-related files and correspondence, and the informed consent documentation of this clinical trial.

